5.2.2 Dose Evaluation Schema

We will perform a VCT for each tumor site to assess quantitatively dose prediction errors (DPEs) and optimization-convergence errors (OCEs) associated with more approximate SECT stopping power mapping. In the VCT, every patient will go through the current clinical workflow for planning and dose delivery, where SECT is the primary image for treatment planning and conventional range uncertainty of 3.5% is employed. The SECT data uses one of the two DECT data sets. The DECT images will be used differently in Arm A and Arm B of the VCT.

In Arm A, patients are treated with treatment plans optimized and calculated on the SECT data. Plan dose is re-calculated for every patient with the clinical plan in a Monte Carlo dose calculation engine for better accuracy. We will use TOPAS, an extension of Geant4 simulation toolkit, as the dose calculation engine.

In Arm B, the DECT data is used for plan optimization and dose calculation. In Arm B1, DECT data is used to estimate the actual dose delivered using the clinical plan based on SECT data. In Arm B2, the plan is re-optimized on DECT data with the conventional uncertainty margin of 3.5% of proton range. In Arm B3, the plan is re-optimized on DECT data with the SPR uncertainties derived from the patient-specific uncertainty model developed.

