1.2 Study Rationale

The aim of this protocol is to refine the accuracy of PT by the use of DECT, in conjunction with novel iterative image reconstruction algorithms, to more precisely determine the tissue properties through which the proton beam path travels.

Plan quality in proton therapy is compromised by lack of accurate knowledge of proton stopping power, giving rise to dose prediction errors (DPEs) and optimization-convergence errors (OCEs). The DPEs are defined as the difference between the dose calculated by the treatment planning system and the actual dose delivered to the patient, mainly affected by the inaccurate prediction in the distal edge of a proton beam. OCE is defined as the difference between a clinically executed plan produced by an optimizer based on dosimetric approximations (e.g., SECT) and a better plan (e.g., based on DECT). Accounting for inaccuracies or uncertainty in proton stopping power, the planning optimizer must include a safety margin for the resulting range uncertainty and perform robust optimization using the distribution of errors. We hypothesize that both DPEs and OCEs arising from SECT SP mapping errors will give rise to measurable changes in clinical outcomes and that this loss of clinical efficacy can be reduced with more accurate estimation of proton stopping power using DECT.

Knowledge gained from the DECT will be used to generate a mock PT plan for comparison purposes. Successful completion of this project is intended to measure potential increases in the accuracy with which cancers can be treated with proton therapy and to reduce the potential incidence of normal tissue toxicity. We will then evaluate whether the additional normal tissue dose sparing achieved in these mock plans could improve outcomes for patients undergoing proton therapy by reducing normal tissue complications or enabling tumor dose escalation in comparison to the more traditional 3-6 mm estimates of range uncertainty from Moyer et al.

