Uncertainty in proton range is incorporated into proton plan optimization in two ways: safety margin and robust optimization. Safety margin involves expanding CTV and OAR contours (generally by 3.5% of proton range) as recommended by ICRU 50 and 62. Recent studies have demonstrated that robust optimization in proton therapy produces more consistent and predictable dose distribution through the whole treatment course. Given the PDFs describing various uncertainties (setup, organ motion, and true vs. apparent SPR values), robust optimization selects multiple worst case scenarios (instances of patient anatomy and SPR assignments) from the ensemble of all possible instances described by the PDFs. The optimizer then optimizes the plan to satisfy the planning constraints and goals simultaneously on the multiple worst-case scenarios. The resultant plan is robust in the sense that acceptable outcomes will be realized even in the face of the most unfavorable random outcomes (positioning and SPR errors) that are likely to occur. In clinical practice, volumetric imaging greatly reduces the uncertainty associated with setup and sheds light on pre-treatment reoptimization of the treatment plan. As the range uncertainty becomes the largest uncertainty in plan optimization, accurate information on proton stopping power helps the optimizer achieve a more optimal plan.

Patient participation will be limited to having a DECT instead of the standard SECT. That single DECT session will be used to generate two treatment plans; one using standard range uncertainty margins and the second using exact measures of tissue density from the DECT to generate a mock treatment plan for comparison. We expect that the mock treatment plan will have tighter margins around the tumor and spare more normal tissue. Eligible patients

will either have lung cancer or cancer of the brain or base of skull. We have chosen these two patient populations because the tumor is adjacent to air densities where range uncertainty is greater, the problem poses the greatest technical challenge, and reducing the projected toxicity to critical structures would be clinically most meaningful (i.e. reducing dose to the esophagus or optic nerve).

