5.2.3 Definitions

DPE. The fractional DPE is $(D_x^{DE,B1} - D_x^{SE,A})/D_x^{DE,B1}$, based on the difference in planned dose (Arm A) and delivered dose (Arm B1), where x is the dose-volume index and the superscript A and B1 denotes the dose plan from Arm A and B1 respectively.

OCE. The fractional OCE is $(D_x^{DE,B2} - D_x^{DE,B3})/D_x^{DE,B2}$, based on the difference in planned dose optimized on DECT with the conventional uncertainty margin (Arm B2) and the SPR uncertainties derived from the patient-specific uncertainty model developed in Arm B3.

Combined. The total change in dose between optimized plans from SECT and DECT data.

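### DECT is both planning map and reference for Arms B2 and B3, so B3's normal-tissue sparing would be reported without its target coverage and TCP under residual DECT error

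*Combined protocol and SAP*

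**What the plan says.** Section 1.2 defines the dose prediction error in general terms: "The DPEs are defined as the difference between the dose calculated by the treatment planning system and the actual dose delivered to the patient". Its hypothesis concerns errors that come from SECT stopping-power mapping, and it holds that "this loss of clinical efficacy can be reduced with more accurate estimation of proton stopping power using DECT". The same section describes the second plan as "using exact measures of tissue density from the DECT to generate a mock treatment plan for comparison" and adds: "We expect that the mock treatment plan will have tighter margins around the tumor and spare more normal tissue".

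Section 5.2.2 sets up the arms. Arm A is the SECT plan with its Monte Carlo recalculation. For B1, "In Arm B1, DECT data is used to estimate the actual dose delivered using the clinical plan based on SECT data". B2 is re-optimised on DECT with the conventional 3.5% uncertainty. For B3, "In Arm B3, the plan is re-optimized on DECT data with the SPR uncertainties derived from the patient-specific uncertainty model developed".

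Section 5.2.3 defines two named contrasts and a combined one:
- DPE is "based on the difference in planned dose (Arm A) and delivered dose (Arm B1".
- OCE is "based on the difference in planned dose optimized on DECT with the conventional uncertainty margin (Arm B2" and the corresponding planned dose in B3. Both terms carry the DECT superscript.
- The combined measure is the total dose change between SECT-optimised and DECT-optimised plans.

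Section 5.3 intends to express a reduction of DPEs and OCEs in clinical terms, and to compare tumor control and complications between Arms A and B. Section 2.2 lists dose-delivery accuracy (b) and simulated patient outcomes (c) among the exploratory objectives. Section 7.0 works with a range uncertainty that falls from 3.5% to 1.0%, not to zero.

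**The concern.** The protocol does not treat DECT as error-free. Section 1.4 claims lower uncertainty, Section 7.0 keeps 1.0%, and B3 needs an uncertainty model of its own. The evaluation in Sections 5.2.2 and 5.2.3 nevertheless contains no step in which a DECT-based plan meets a stopping-power map other than its own.

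This matters mainly for B3. According to Section 1.1, the 3.5% is there to protect tumor coverage. If B3's patient-specific uncertainty is smaller, B3 gives up some of that protection in exchange for sparing. OCE, the combined measure and NTCP would record the gain. The possible cost, lost coverage or TCP when the DECT map is wrong by more than B3 allows for, has no stated place in the results. The lung indices named in Section 7.0 (heart V30, esophageal V60, mean heart dose, lung V20) are all normal-tissue indices.

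At stake are exploratory objectives (b) and (c), and the use of these data to design the broader trial mentioned in Section 6.3. Its designers would see the benefit of B3 over B2 without the matching target-side result.

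**Working it through.** **1. Which plan is scored on which map (Sections 5.2.2 and 5.2.3)**

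| Arm | Planned on | Scored on | Used in |
|---|---|---|---|
| A | SECT, 3.5% | SECT | DPE, as planned dose |
| B1 | SECT, 3.5% (the A plan) | DECT | DPE, as delivered dose |
| B2 | DECT, 3.5% | DECT | OCE, as planned dose |
| B3 | DECT, patient-specific uncertainty | DECT | OCE, as planned dose |

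B1 is the only row in which the two maps differ. The text names no other scoring map for B2 or B3.

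**2. What a DPE for a DECT plan would be.** The DPE in Section 5.2.3 is (delivered − planned)/delivered. With DECT as the reference, and the same dose engine for both terms, the delivered and planned doses of plan p (B2 or B3) are both D_x^{DE,p}. The result is (D_x^{DE,p} − D_x^{DE,p})/D_x^{DE,p} = 0, whatever the quality of the DECT map.

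**3. The plan's own margin figure.** Section 1.1 equates 3.5% with about 4 mm at a 12 cm range. Check: 0.035 × 120 mm = 4.2 mm. It agrees.

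**4. Geometry of a smaller margin (illustration).** Assume that B3's uncertainty acts like a 1.0% range margin. The 1.0% is from Section 7.0; Section 5.2.2 does not fix B3's value.
- B3 margin at 12 cm: 0.010 × 120 = 1.2 mm.
- Margin removed relative to B2: 4.2 − 1.2 = 3.0 mm.

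Uncovered distal distance = max(0, range error − margin) × range:

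| Range shortfall | B2 (3.5%) | B3 (1.0%) |
|---|---|---|
| 1.0% | 0 mm | 0 mm |
| 3.5% | 0 mm | (0.035 − 0.010) × 120 = 3.0 mm |

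**5. Sensitivity of that figure**
- If B3's uncertainty were 2.0%, the margin removed at 12 cm would be 0.015 × 120 = 1.8 mm. At 3.0% it would be 0.005 × 120 = 0.6 mm.
- Section 1.1 also cites margins of 3 to 6 mm. At 3.5% these correspond to ranges of 3/0.035 = 85.7 mm and 6/0.035 = 171.4 mm. The 2.5-point difference is then 0.025 × 85.7 = 2.1 mm to 0.025 × 171.4 = 4.3 mm.

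These are distances, not doses. The documents give no distribution of residual DECT error and no dose gradients, so no change in coverage, TCP or NTCP can be derived from them.

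**The case against.** The strongest reply is that the scope is intended. Sections 1.2 and 5.2.2 tie DPE and OCE to errors of SECT mapping, and Section 5.2.1 says openly that the research images stand in for the patient. Under that premise A versus B1 is the right DPE, and its reduction can simply mean removing the SECT error. This stands: the definition of DPE is not a mistake and need not change. It does not, however, supply any information on the delivery accuracy of a DECT plan, which objective (b) would naturally be taken to include.

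Second, Section 1.2 describes robust optimisation over worst-case stopping-power scenarios, and B3 takes its uncertainties as an optimiser input. This also largely stands for errors inside the model; the geometry above gives 0 mm uncovered at 1.0%. But an optimiser input is not a reported result, and it protects only as far as the model is right.

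Third, a reader might infer that tumor control is left out altogether. The documents do not support that. Section 5.3 plans a tumor-control comparison, and the index x in Section 5.2.3 is not restricted to normal tissue. Only the version under residual error is unstated.

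Fourth, a reader might take the 3.0 mm as an expected loss of coverage in B3. That is not supported either. Every non-zero shortfall comes from giving DECT a 3.5% error, and no passage attributes such an error to DECT.

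Finally, Figure 1 may show a further step. If it does, one sentence in Section 5.2.2 would settle the point.

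**Conclusion.** The point holds in a limited form. In the text, DECT is both the planning map and the reference for B2 and B3, so the delivery error of a DECT plan is zero by construction. No stated endpoint shows B3's target coverage or TCP under residual DECT stopping-power error or a misspecified uncertainty model. If B3's uncertainty is below 3.5%, its sparing relative to B2 would be reported one-sidedly.

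The size of any dosimetric or outcome effect cannot be computed from the documents. The geometric illustration (3.0 mm of margin removed at 12 cm; 0 mm uncovered at a 1.0% error, 3.0 mm at 3.5%) assumes that B3 behaves like a 1.0% range margin and uses 3.5% purely as a stress bound. Nothing here shows that B3 would fail or that its sparing is not genuine.

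The limitation concerns exploratory objectives (b) and (c) and the design of a later trial. The primary objective in Section 2.1 is not affected. This is a cheap improvement, worth considering.

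**What to change.** Keep Arms A and B1 and the existing DPE and OCE contrasts as they are. B1 should stay out of the perturbation exercise: shifting it against Arm A would mix SECT-DECT disagreement with the shift, and the result would not be like-for-like with B2 and B3.

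- **Section 5.2.2, add:** *The fixed B2 and B3 plans will be recalculated on the DECT SPR map perturbed by plus and minus the patient-specific SPR uncertainty used in B3, and by plus and minus 3.5% as a stress bound, with the same perturbations for both plans.*
- **Section 5.2.3, add:** for plan p (B2 or B3) and scenario s, the change (D_x^{s,p} − D_x^{DE,p})/D_x^{s,p}, in the form of the existing DPE but named as a sensitivity measure and not as measured delivery error.
- **Section 5.3, add:** worst-case target coverage and TCP, reported beside each normal-tissue index and NTCP difference, with the model-based pair and the 3.5% pair shown separately.
- **Limitations to state:** DECT is the reference map, so all SECT-DECT disagreement is attributed to SECT; and the scenarios do not validate DECT independently.

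These are evaluation scenarios only; no clinical margin is proposed.

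Cost: no added patients, scans or imaging dose. There are 2 plans × 4 scenarios = 8 extra Monte Carlo runs per patient, on top of about 4 now (A, B1, B2, B3). With 20 to 25 patients per site (Section 7.0), that is 8 × 40 to 8 × 50 = 320 to 400 runs for two site groups (Section 1.2), or 8 × 60 to 8 × 75 = 480 to 600 for three (Section 2.2). The number of groups is an assumption, and the documents give no run time. The other costs are analyst time and possibly a smaller apparent benefit of B3.

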5.2.3 Definitions

DPE. The fractional DPE is $(D_x^{DE,B1} - D_x^{SE,A})/D_x^{DE,B1}$, based on the difference in planned dose (Arm A) and delivered dose (Arm B1), where x is the dose-volume index and the superscript A and B1 denotes the dose plan from Arm A and B1 respectively.

OCE. The fractional OCE is $(D_x^{DE,B2} - D_x^{DE,B3})/D_x^{DE,B2}$, based on the difference in planned dose optimized on DECT with the conventional uncertainty margin (Arm B2) and the SPR uncertainties derived from the patient-specific uncertainty model developed in Arm B3.

Combined. The total change in dose between optimized plans from SECT and DECT data.

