2.2 Exploratory Objectives

To assess the impact of DECT tissue property mapping on

- a.) plan quality
- b.) dose-delivery accuracy, and
- c.) simulated patient outcomes

for locally advanced lung, H&N and brain tumor patients treated with proton therapy.

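### The OCE formula in 5.2.3 captures only the uncertainty-margin part of the SECT optimization loss described in 1.2 and 5.2.2; the part from optimizing on the SECT map has no formula

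*Combined protocol and SAP*

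**What the plan says.** Section 1.2 introduces OCE as the "difference between a clinically executed plan produced by an optimizer based on dosimetric approximations (e.g., SECT) and a better plan", giving DECT as the example of the better plan. Its hypothesis is that "both DPEs and OCEs arising from SECT SP mapping errors will give rise to measurable changes in clinical outcomes". Section 5.2.2 says the virtual trial will assess "optimization-convergence errors (OCEs) associated with more approximate SECT stopping power mapping".

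Section 5.2.2 then sets out four dose calculations per patient:
- Arm A: "patients are treated with treatment plans optimized and calculated on the SECT data".
- Arm B1: "In Arm B1, DECT data is used to estimate the actual dose delivered using the clinical plan based on SECT data".
- Arm B2: a new optimization on DECT at the conventional 3.5%.
- Arm B3: a new optimization on DECT with SPR uncertainties from the patient-specific model.

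Section 5.2.3 defines the fractional DPE as (B1−A)/B1 and the fractional OCE as (B2−B3)/B2, the latter "based on the difference in planned dose optimized on DECT with the conventional uncertainty margin (Arm B2") and the patient-specific alternative (Arm B3). A third quantity, *Combined*, is described in one sentence as the overall dose change between SECT-optimized and DECT-optimized plans, without a formula. Section 5.3 carries the reduction of DPE and OCE into tumor-control and complication models.

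**The concern.** The words in 1.2 and 5.2.2 require a SECT-optimized plan on one side of the OCE comparison. The formula has none: both of its terms are DECT-optimized plans that differ only in how range uncertainty is handled. A reader of the results would take the number reported as OCE to be the whole optimization loss from planning on SECT, when it is one component of that loss.

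The hypothesis in 1.2 is about OCE that arises from SECT mapping errors, and the exploratory aim in 2.2 is "To assess the impact of DECT tissue property mapping on" plan quality, delivery accuracy and simulated outcomes. If the component tied most directly to map accuracy is left out, the reported OCE answers a narrower question than the one posed, and it could be too large or too small as a summary of the total.

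**Working it through.** **Inputs.** The arm descriptions come from 5.2.2 and the formulas from 5.2.3. The documents report no dose for any arm, so there is no stated figure to reproduce. The check is algebra, followed by an illustration with assumed values.

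**Step 1: what each formula contains.**

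| Contrast | Plan optimized on | Dose evaluated on | Uncertainty used | Formula in 5.2.3 |
|---|---|---|---|---|
| A to B1 | SECT in both | SECT, then DECT | 3.5% in both | DPE |
| B1 to B2 | SECT, then DECT | DECT in both | 3.5% in both | none |
| B2 to B3 | DECT in both | DECT in both | 3.5%, then patient-specific | OCE |

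DPE compares one clinical plan calculated on two image sets, so it carries no optimization effect. The only step in which the image used for optimization changes is B1 to B2, and it has no formula.

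**Step 2: decomposition.** For any dose-volume index,

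B1 − B3 = (B1 − B2) + (B2 − B3).

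The left side is the executed SECT plan, evaluated on DECT, against the best DECT plan. That is the comparison 1.2 describes. The written OCE takes only the second term on the right, so it does not change with A or B1.

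**Step 3: illustration.** Assume relative units B2 = 100 and B3 = 98, and let B1 vary. None of these values comes from the documents.

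| B1 | Written OCE, (B2−B3)/B2 | Optimization-image part, (B1−B2)/B1 | Total, (B1−B3)/B1 |
|---|---|---|---|
| 100 | 2/100 = 2.0% | 0/100 = 0.0% | 2/100 = 2.0% |
| 103 | 2.0% | 3/103 = 2.9% | 5/103 = 4.9% |
| 105 | 2.0% | 5/105 = 4.8% | 7/105 = 6.7% |
| 110 | 2.0% | 10/110 = 9.1% | 12/110 = 10.9% |

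The written OCE stays at 2.0% throughout. The sign of B1−B2 is not fixed by the documents either; if it were negative, the written OCE would exceed the total.

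**Step 4: additivity.** Absolute differences add, as in step 2. The fractions do not, because their denominators differ; they chain as 1 − [1 − (B1−B2)/B1] × [1 − (B2−B3)/B2] = (B1−B3)/B1. For B1 = 105: 1 − (100/105) × (98/100) = 6.7%, which agrees with the table.

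**The case against.** The strongest reply is that B2 versus B3 is itself a SECT-related loss. Section 1.1 attributes the range margins to SECT planning, 1.2 says the optimizer must carry a safety margin because stopping power is uncertain, and 5.2.2 applies 3.5% in the SECT workflow. Section 1.2 also describes two plans per patient, "one using standard range uncertainty margins and the second using exact measures of tissue density from the DECT", which resembles B2 versus B3, and 7.0 bases its first power statement on reducing the uncertainty from 3.5% to 1.0%. This stands. A reader might infer that the written OCE shows nothing about the loss from SECT, and the documents do not support that: it captures the margin component and should be kept.

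A reader might also infer that the SECT-to-DECT change will go unreported. That is too strong as well. *Combined* covers the change in words, and B1−B2 can be recovered by subtraction from doses already planned. What remains is that no formula isolates it and the label OCE excludes it.

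A third inference is that the unnamed arms in *Combined* and 5.3 leave the results open to choice. Figure 1 illustrates the virtual trial but is not visible in the text available and may label the contrasts, and 5.3 can be read as A against each B arm. Those points call for clarification only. The mismatch between the OCE wording and its formula does not depend on the figure.

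Finally, 1.2 uses SECT and DECT as examples, so it is not a strict operational definition. But 5.2.2 repeats the attribution to SECT mapping without that hedge.

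**Conclusion.** The concern holds in a limited form. The OCE formula in 5.2.3 measures the uncertainty-margin component (3.5% versus patient-specific) and omits the component from optimizing on the SECT stopping-power map, which 1.2 and 5.2.2 include. This follows from the arm descriptions and the algebra alone and needs no assumed numbers.

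The size of the omitted component cannot be stated. The percentages in the illustration show only that the written OCE is insensitive to it. Nor do the documents support equating it with the 2%–3% detectable change in 7.0, because that section names no arms. The total proposed below treats the DECT-calculated dose in B1 as the delivered dose, which is the plan's own convention.

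The stakes are moderate: DPE and OCE serve the exploratory objectives in 2.2, while the primary objective concerns the distributions of radiological quantities. It should still be corrected before analysis, because the hypothesis in 1.2 is stated in terms of OCE.

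**What to change.** In 5.2.3:
1. Keep (B2−B3)/B2, labelled as the uncertainty-margin component of OCE.
2. Add (B1−B2)/B1 as the optimization-image component: the SECT-optimized plan evaluated on DECT against the DECT-optimized plan at the same 3.5%.
3. Define total OCE as (B1−B3)/B1, which matches the description in 1.2, and note that the two components add in absolute dose but not as fractions.

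As clarification only, write *Combined* with named arms as A versus B3. In absolute dose this is A−B3 = (A−B1) + (B1−B3), that is, the prediction error plus total OCE. The sign needs stating, since 5.2.3 writes the DPE numerator as B1−A. In 5.3, state that A is compared with each of B1, B2 and B3.

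The cost is wording plus one or two more reported contrasts per dose-volume index. Doses for all four arms are already planned for every patient, so no new scans, plans or patients are needed.
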